4.1 Inclusion criteria

- (1) Aged between 18 and 75 years old
- (2) Imaging and puncture pathology showed dental cystic lesions of the mandible
- (3) Cystic lesions greater than or equal to 2cm in diameter and affecting the inferior alveolar nerve
- (4) Lesions of new or recurrent cysts, or odontogenic cystic lesions that are still greater than or equal to 2cm after other treatments such as fenestration and affecting the lower alveolar nerve
- (5) No serious systemic diseases, can tolerate general anesthesia
- (6) Patients who intend to undergo surgical treatment for mandibular bone cysts under general anesthesia
- (7) There was no inferior alveolar nerve injury before operation
- (8) Did not participate in other clinical trials within the past 30 days
- (9) Patients who voluntarily participate in the project and sign informed consent

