5.2 Research and design process

5.2.1 Study the specific implementation process

This study started from the recruitment of subjects, oral panoramic film, maxillofacial CT and other imaging examinations were performed to confirm the diagnosis. After preliminary screening according to the inclusion and exclusion criteria, patients were enrolled after signing the informed consent letter. Endoscopic and navigational techniques were used for surgical treatment. This study referred to A prospective study by Abdullah Hanfesh¹⁵ et al to evaluate the function of the inferior alveolar nerve: the bilateral mandibular and lower lip were divided into four areas: area A, area B, area C, and area D. The four areas will be lightly touched, acupuncture, cold and hot stimulation, and two-point discrimination detection four times respectively. The detection situation of each area will be recorded. The scoring criteria for each test are as follows.

[figure not shown]

Figure 1. Area diagram¹⁵
 A: Upper right lip B: Upper left lip C: Right jaw D: Left mandible

Light touch: Cotton wool is used for light touch detection. The score range is 0-4, with 4 indicating no nerve damage.

Table 1 Light touch stimulus rating table

Sign	Score
Completely unresponsive to stimuli	0
Severe loss of perception	1
Mild irritation is almost imperceptible	2
Compared with pre-operation slight stimulation can still be perceived	3
Compared with pre-operation there was no difference, normal perception of mild stimulation	4

Acupuncture: Detection is performed using dental probe stimulation on a scale of 0-1, with 1 indicating no nerve damage.

Table 2. Acupuncture stimulation rating table

Sign	Score
Completely unresponsive to stimuli	0
Produces a sharp tingling sensation to stimuli	1

Figure 2 Lower alveolar nerve function measured by cotton wool¹⁵

Figure 3. The function of inferior alveolar nerve was detected by acupuncture¹⁵

Hot and cold stimulation: Test tubes filled with hot water (45-50 ° C) and filled with ice water were used to detect hot and cold stimulation, respectively. The score range was 0-1, with 1 indicating no nerve damage.

Table 3. Cold and heat stimulation rating table

Sign	Score
Completely unresponsive to stimuli	0
Develop a cold/hot sensation to stimuli	1

Figure 4. The function of inferior alveolar nerve was measured by heat and cold stimulation¹⁵

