Two-point discrimination test: The distance between two points can be distinguished using a vernier caliper. The score ranges from 0 to 5, with 5 indicating no nerve damage.

Table 4: Two-point discrimination measurement rating table

Sign	Score
The distance between the two ends of the vernier caliper is > 15mm	0
The distance between the ends of the vernier caliper is 10-15mm	1
The distance between the ends of the vernier caliper is 9-10mm	2
The distance between the ends of the vernier caliper is 7-9mm	3
The distance between the ends of the vernier caliper is 5-7mm	4
The distance between both ends of the vernier caliper is less than 5mm	5

Figure 5 Vernier calipers measure the distance between two points¹⁵

Inferior alveolar nerve function was detected before and 1 month after surgery. Light touch detection 4 points, acupuncture detection 1 point, hot and cold stimulation 1 point, two-point discrimination detection 5 points showed no nerve damage. Any other score for any of the above is considered to be nerve damage.

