5.2.3 Research schedule

Interview	Screening period	Before operation	Operation	Follow-up visit			
	V1	V2	V3	V4	V5	V6	V7
Follow-up time	1 day before enrollment	Enrollment day	Day after V2	1 week after surgery	One month after surgery	Three months after surgery	1 year after surgery
Sign informed consent	✓						
Inclusion/exclusion criteria	✓						
Demographic data	✓						
Medical history	✓						
Neural test score		✓			✓		
Physical examination	✓	✓	✓	✓	✓	✓	✓
Vital sign	✓	✓	✓	✓	✓	✓	✓
Electrocardiogram	✓						
Blood routine examination	✓						
Blood biochemistry	✓						
Liver function	✓						
Coagulation function	✓						
Imaging examination	✓				✓		✓
Pathological examination			✓				
Epidemiological examination	✓						
Adverse event evaluation			✓	✓	✓	✓	✓

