5.4.2 Data Analysis Set

Statistical analysis will be performed using SAS statistical analysis software (V.9.4, SAS Institute). If there is no special explanation, unilateral test will be used for the main index, and the control error α is 0.025; bilateral test will be used for the other indicators, and the error α is =0.05. If you need to calculate confidence intervals, calculate bilateral 95% confidence intervals unless otherwise specified.

- (1) full analysis set (FAS) : comprised of all subjects who underwent surgical treatment and were evaluated for efficacy. The data set is derived from all subjects by eliminating subjects in a minimal and reasonable way.
- (2) safety analysis set (SS) : A group of people who have received surgical treatment and have safety evaluation data. In the safety analysis, all patients will be analyzed according to the actual surgical group received.
- (3) per-protocol set (PPS) : all subjects who met the protocol and did not use concomitant drugs that affected the effectiveness evaluation, had good medication compliance (between 80% and 120%), and excluded subjects who had a major protocol violation and were judged to have a significant impact on the results. All trial protocol deviations that result in subjects being excluded from the conformance protocol set will be detailed in the Statistical Analysis Plan (SAP) and completed prior to data locking.

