5.4.3 Statistical Analysis Plan

Data description of statistical analysis, analysis methods of primary/secondary indicators/safety indicators, statistical correction methods, bias control, stratification/subgroup/sensitivity analysis, etc.

Demographic and other baseline characteristics: Based on FAS set, demographic data, medical history, vital signs and other baseline data were statistically described. The mean, standard deviation, minimum, maximum and median values were given for measurement data (age, BMI, body weight, blood pressure, etc.). Counting data (gender, tobacco and alcohol history, etc.) give the frequency and corresponding percentage.

Analysis of efficacy index: The main evaluation index (postoperative nerve injury rate) was estimated by point and the bilateral 95% confidence interval was estimated by Clopper-Pearson exact probability method. If the lower limit of the 97.5%

confidence interval is lower than the postoperative nerve injury rate of the historical control, it is considered that the efficacy of the navigational endoscopy group is better than the historical control. Secondary efficacy indicators were analyzed using FAS and PPS analysis sets. For postoperative recurrence indicators, the median postoperative recurrence time and bilateral 95% confidence interval were calculated. For the rates of each index, point estimation was performed and the Clopper-Pearson accurate probability method was used to estimate the bilateral 95% confidence interval. For the continuity index, if it conforms to the normal distribution, its mean and bilateral 95% confidence interval are calculated based on the normal distribution method, otherwise based on hundreds. The quantile method calculates the median and bilateral 95% confidence intervals.

Analysis of safety indicators: SS sets were used to make statistical descriptions of the incidence of adverse events/serious adverse events, adverse reactions and other safety indicators, and to list and describe the details of each adverse event for each subject, including the type and severity of adverse events. Laboratory indicators, vital signs, electrocardiogram and other safety-related indicators were compared and evaluated before and after treatment, and clinical evaluation (normal, abnormal no clinical significance, abnormal clinical significance, no investigation) was given before and after treatment for statistical description.

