The processing principle of missing/deleted/lost data: LOCF (last observation carried forward) method was adopted to fill in the analysis of main indicators, that is, the last observed data was used to fill in the data that failed to observe the main indicators. Secondary indicators and security indicators are not filled.

VI. Research and intervention

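### LOCF on the primary endpoint can fill a missing 1-month nerve test only with the pre-operative result, so any untested patient kept in the analysis would normally count as uninjured

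*Protocol*

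**What the plan says.** Section 5.4.3 prescribes LOCF for the primary indicator and no filling for the secondary and safety indicators. For the primary indicator, "the last observed data was used to fill in the data that failed to observe the main indicators".

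Section 5.2.1 gives the test times: "Inferior alveolar nerve function was detected before and 1 month after surgery". The schedule in section 5.2.3 agrees. Its row "Neural test score" is ticked only at V2 (before surgery) and V5 (1 month), and the 1-week visit has no nerve test. Each test visit has several items: "The four areas will be lightly touched, acupuncture, cold and hot stimulation, and two-point discrimination detection four times respectively". Inclusion criterion 7 in section 4.1 reads "There was no inferior alveolar nerve injury before operation".

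On the analysis population, section 5.4.2 defines the full analysis set (FAS) as "comprised of all subjects who underwent surgical treatment and were evaluated for efficacy", and then adds "The data set is derived from all subjects by eliminating subjects in a minimal and reasonable way". Section 5.4.3 says "Secondary efficacy indicators were analyzed using FAS and PPS analysis sets" but names no set for the primary endpoint.

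Section 2.2.1(4) lists failed repair of a nerve tear among the reasons for withdrawal. Sections 2.2.1(4) and 7.2 make follow-up after withdrawal optional.

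**The concern.** The endpoint is an injury caused by the operation. LOCF needs an earlier value that says something about the missing one, and here the only earlier value dates from before the exposure. For an operated patient who misses V5, the rule turns not examined into not injured.

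The trial has one arm and its conclusion rests on one rate set against a historical benchmark. No control arm is subject to the same filling, so the error does not cancel. Each filled patient adds to the denominator and normally nothing to the numerator, which lowers both the estimate and its upper confidence limit.

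Missing results may also be linked to the outcome. A patient withdrawn after a failed nerve repair, and then not tested at 1 month, could be entered as uninjured.

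**Working it through.** **Inputs**
- Benchmark 32%, expected rate 20% (section 5.1).
- One-sided alpha 0.025, power 80%, 109 patients raised to 122 for 10% loss (section 5.4.1).
- Two-sided 95% Clopper-Pearson interval (section 5.4.3).
- Section 5.4.1 words the rates as 20% and 12%, so a 20% benchmark is also shown.
- Section 5.2.2 counts 122 people before screening, so fewer may be operated. The value 116 is used as an illustration.

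**Assumptions.** Untested patients are kept and filled as uninjured. Results are missing at random. Success means that the upper limit lies below the benchmark. The number missing, m, is not given in the protocol and is varied. The value 13 is the upper end: it puts the whole planned loss before month 1, and section 5.4.1 does not say when losses occur.

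**Step 1: reproduce the sample size.**
n = [1.960·√(0.32·0.68) + 0.842·√(0.20·0.80)]² / 0.12² = 108.7, so 109. Then 109/0.9 = 121.1, so 122. The same formula with 20% against 12% gives 175. The stated size therefore belongs to 32% against 20%, and 32% is the main benchmark here.

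**Step 2: what can be carried forward.** The test times are V2 and V5. If V5 is missing, only V2 remains, and criterion 7 makes V2 normally uninjured.

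**Step 3: effect on the estimate.** The expected rate is p·(N−m)/N. With N = 122 and m = 13, a true 32% is reported on average as 0.32·109/122 = 28.6%, and a true 20% as 17.9%.

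**Step 4: effect on type I error.** Let c be the largest number of injuries in N whose upper limit is below p0. With LOCF, only N−m patients can contribute an injury, but c is still set by N:

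false success = P(X ≤ c), X ~ Binomial(N−m, p0)

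For N = 122 and p0 = 32%, c = 28: 28/122 has upper limit 31.4%, and 29/122 has 32.3%.

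| Benchmark, operated | c | m=0 | m=3 | m=4 | m=6 | m=13 |
|---|---|---|---|---|---|---|
| 32%, 122 | 28 | 1.8% | 2.8% | 3.1% | 4.1% | 9.3% |
| 32%, 116 | 26 | 1.5% | 2.3% | 2.7% | 3.5% | 8.4% |
| 20%, 122 | 15 | 1.8% | 2.4% | 2.7% | 3.2% | 6.1% |

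The nominal 2.5% is first passed at m = 3 in the first row and at m = 4 in the other two. The exact crossing depends on binomial discreteness. Against 32%, with any number operated from 109 to 122, it falls between 1 and 4 missing.

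**Step 5: an example.** Of 122 operated, 119 are tested and 28 are injured. The observed result 28/119 has upper limit 32.2% and fails. After LOCF, 28/122 has upper limit 31.4% and succeeds. Three patients never examined after surgery change the conclusion.

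**Step 6: the rule as written.** Section 5.4.3 compares the lower limit with the benchmark. With a 95% interval, N = 122 and none missing, that gives 97.7% false success at a true 32%. This is a separate error. The figures above describe what LOCF does once it is corrected.

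**The case against.** The strongest reply is that the harm is conditional. A pre-operative test cannot evaluate the operation, so the plainest reading of evaluated for efficacy in section 5.4.2 excludes anyone without V5, and then nothing is inflated. This is right as far as it goes. But on that reading the LOCF rule has almost nothing to act on, at most a missing item within V5, and it sits beside an instruction to exclude as few patients as possible. A fill-in rule written for the primary endpoint suggests that such patients were meant to stay. The text supports both readings, and they give different results.

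A second reply is that few patients will be lost by 1 month. Sections 6.3 and 7.3 provide for a return visit, telephone contact and several contact persons, and the 13-missing case is an extreme. This also stands in part: with 3 missing of 122 the excess over 2.5% is only 0.3 points, and the example in step 5 is a boundary case. Still, 1 to 4 missing are enough to pass the nominal level against 32%, and the bias runs towards success.

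A third reply is that the lower-limit rule is by far the larger defect. That is true, but correcting it leaves the LOCF bias in place.

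Leaving the matter to the SAP is no answer, because the protocol has already chosen the method.

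**Conclusion.** The rule is wrong as written and must be fixed. With the test done only before surgery and at 1 month, LOCF cannot supply a valid post-operative result, and nothing else in the protocol repairs this.

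If untested patients are kept, false success against 32% with 122 operated is 2.8% with 3 missing and 9.3% at the upper end of 13, compared with 1.8% when none are missing. If they are excluded there is no inflation, but sections 5.4.2 and 5.4.3 then contradict each other in purpose.

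The sizes rest on an upper-limit success rule, missing at random, and assumed numbers missing. Inflation would be larger if injured patients are missing more often; the protocol gives no figure for that.

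**What to change.** 1. Delete LOCF for the primary endpoint in section 5.4.3.
2. Name the primary analysis set and reconcile it with section 5.4.2: operated patients with an observed 1-month nerve test, plus any patient with a documented unrepaired nerve tear and no test, counted as injured.
3. Do not fill a single missing V5 item from before surgery. Under section 5.2.1, any observed below-normal item already counts as injury. If the remaining items are all normal, treat the result as unresolved under point 5.
4. State in sections 2.2.1(4) and 7.2 that the 1-month test will be sought for all operated patients, including those withdrawn.
5. Show all remaining missing or unresolved results, including an untested repaired tear, in a sensitivity analysis running from all uninjured to all injured. Details can go in the SAP.

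Do not make all missing equal injured the primary analysis. With 122 operated and a true rate of 20%, power is P(X ≤ 28−m), X ~ Binomial(122−m, 0.20): 66% with 3 missing and 44% with 6.

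**Cost.** The change is wording, and the reported rate may be slightly less favourable. With 109 to 122 tested and no tears to add, alpha is 1.5% to 2.5% and power at a true 20% is 77% to 85%. If fewer are operated, power can fall further: 76.6% with 103 tested, and at its lowest 73.4% (105 tested) over the range 103 to 122.

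Counting untested tears also costs power. With two of them and 120 tested, success allows at most 26 tested injuries instead of 28, and power at 20% among the tested is 72% instead of 85%. That reflects two known injuries: 28/120 alone succeeds (upper limit 31.9%), while 30/122 fails (33.2%). Bias from other injured patients going missing remains possible, which is why the sensitivity analysis is needed.

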6.1 Study intervention content

All enrolled patients underwent blood routine, liver function, heart function, blood biochemistry, urine routine, stool routine, coagulation function, electrocardiogram, chest film, maxillofacial imaging and other related examinations to ensure the safety of general anesthesia. Preoperative copies of the patient's maxillofacial imaging data were digitally designed, professional software was used to segment cystic lesions and segment the inferior alveolar nerve together, and then the data was imported into the navigation system. After general anesthesia, gingival trapezoidal incision or modified trapezoidal incision was made in the area of the cyst, and the flap was turned to expose the bone surface. The bone window was opened with electric grinding and drilling system, and the lesions were initially cured with curette immediately after the window opening. The occlusal surface and the internal and external sides were mainly treated. The surgeon placed the mandibular reference frame in the mandibular anterior tooth area, and used the navigation probe under the guidance of navigation to accurately locate the anterior cavity of the capsule, the apex of the root of the tooth and the ascending branch of the mandible. After accurate positioning was obtained, the navigation adapter was loaded onto the endoscope to locate the lesions in all directions and the inferior alveolar nerve under visual

conditions, and further precisely curettage the lesions in the cystic cavity with the assistance of the adapter.

6.2 Preparation/handling/storage/Responsibilities

Any drug use or adverse reactions must be recorded in the patient's medical record and recorded at the appropriate location in the CRF.

6.3 Study intervention compliance

The subjects were asked to return to the research center one month after surgery for lower alveolar nerve function detection. The subjects were required to return to the research center for maxillofacial imaging examination at 1 month, 3 months, 6 months, 1 year and 2 years after surgery to determine whether the cyst recurred and whether there was new bone formation in the cystic cavity. During the same period of follow-up, whether the oral wound healed in one stage, whether there was fluid seepage or suppuration. The compliance of the study can be verified according to the review status of the subjects. In the later follow-up, members of the research team must conduct telephone follow-up communication with the subjects and reasonably arrange the time of the subjects' review and visit.

6.4 Combination Therapy

Subjects with diseases requiring long-term drug control, such as hypertension, diabetes, and coronary heart disease, should be evaluated by investigators and relevant specialists to determine the impact of the disease and related research protocols and determine the dosage and duration of adjuvant medication.

6.4.1 Rescue

The life risk of the subjects during the implementation of the clinical study protocol should be implemented according to the clinical rescue protocol, such as cardiopulmonary resuscitation, emergency airway management, and emergency surgical treatment. The relevant records during hospitalization should be recorded in the medical record system, and the occurrence after discharge should be recorded in the adverse event record table. Meanwhile, researchers should analyze the cause of rescue. As to whether it is related to the research and discussed, the discussion is recorded in the rescue record simultaneously.

VII. Study intervention discontinuation or Subject discontinuation and withdrawal

7.1 Study intervention discontinued

During the perioperative period of this study, if the number of patients with serious complications such as anesthesia, serious postoperative infection or bleeding, respiratory distress caused by severe edema of surrounding tissues, nerve lacerations and other serious complications reached 30% of the participants, the study should be

suspended, and the safety of surgical methods of the study protocol should be discussed to determine whether to adjust the study surgical protocol, and follow-up should be conducted during the suspension of the study. Follow-up records of the original subjects were maintained.

7.2 Subject discontinuation/withdrawal from study

When subjects suspend or withdraw from the study due to dissatisfaction with the therapeutic effect of the study program or their own financial reasons, they should communicate with them to encourage them to actively treat the treatment and help them apply for public welfare funds to complete the treatment. In the perioperative period, if serious complications of anesthesia, serious postoperative infection or bleeding, respiratory distress caused by severe edema of surrounding tissues, nerve tears and other serious complications reached 30% of the number of subjects, the study should be suspended, and the safety of the surgical method of the study protocol should be discussed to determine whether to adjust the study surgical protocol, and follow-up should be conducted during the suspension of the study. Follow-up records of the original subjects were maintained. In the case of clear withdrawal, the investigator may continue to complete the follow-up without the study intervention.

7.3 Loss of access (measures to reduce loss of access and data loss due to loss of access)

After the enrollment of subjects, the researchers should keep the contact information of multiple subjects and the contact information of subjects' families. After the subjects are discharged from hospital, the researchers should actively contact the subjects by phone, timely understand the condition of the subjects, and arrange the subjects to be admitted to the hospital for the next stage of treatment in advance.

VIII. Adverse Events and unexpected events

An adverse event (AE) is an adverse medical event that occurs after a subject receives treatment, but is not necessarily causally related to the treatment. An adverse event may be any adverse and unexpected sign (including abnormal laboratory findings), symptom, or disease associated with the use of the treatment, regardless of whether it is related to the treatment. It includes, but is not limited to:

- (1) exacerbation of disease that existed before the study treatment was used;
- (2) Increased frequency or severity of paroxysmal events that existed before the study treatment was used;
- (3) abnormal changes detected or diagnosed after the study of treatment use, although such abnormal changes may have existed before treatment;
- (4) Exacerbation of disease or symptoms that were already persistent before the study began.

Causal relationship between adverse events and treatment measures: In the trial, researchers should conduct comprehensive analysis according to the specific

circumstances of adverse events and subjects' past history, concomitant diseases and concomitant medication, etc., to determine the relationship between adverse events and treatment measures. The relationship between adverse events and treatment measures was classified as "definitely related, it may well be relevant, it may be relevant, it may not be relevant and it may not be relevant."

- (1) Unrelated: Adverse events were not associated with treatment.
- (2) May not be relevant: the occurrence of an adverse event is more likely to be related to other factors, such as co-medication or concomitant disease, or the timing of the event indicates that it is unlikely to be causally related to the treatment.
- (3) May be related: The occurrence of adverse events may be caused by therapeutic measures. Cannot rule out whether other Causes, such as: drug combination or concomitant disease. The occurrence of adverse events and treatment measures have a reasonable time sequence, and the causal relationship between the events and treatment measures cannot be ruled out.
- (4) Likely related: The occurrence of adverse events may be caused by therapeutic measures. The occurrence and treatment measures are Reasonable chronological order.
- (5) Definitely relevant: the type of adverse event has been identified as a result of the treatment and cannot be otherwise justified

Explain, for example, drug combinations and concomitant diseases. The timing of the event strongly suggests causality. The criteria for judging the severity of adverse events can refer to the following criteria:

- (1) Mild: mild symptoms or signs but tolerable.
- (2) Moderate; Symptoms are significant enough to interfere with normal life.
- (3) Severe: severe symptoms, has been unable to carry out normal activities.

All information about adverse events, whether referred to by the patient, discovered by the investigator, or discovered by physical examination, laboratory examination, etc., should be recorded in the study medical record and case report form. During the trial, the occurrence time, duration, symptoms, signs and severity, measures taken and outcome of adverse events should be carefully observed and recorded

And the relationship with treatment measures should be assessed, and appropriate follow-up should be conducted. Possible adverse events include:

(5) Accidental risk of general anesthesia: After patients receive general anesthesia, due to individual differences of patients, abnormal response to drugs may lead to severe suppression of respiratory and circulatory functions and malignant hyperthermia, etc., which can be life-threatening in severe cases. During anesthesia, various adverse reflexes may induce cardio-cerebrovascular accidents or cardiac and respiratory arrest, leading to death. In the event of anaesthesia related adverse reactions, clinical treatment should be performed as a complication of normal surgery, while the patient's medical record is detailed and the possibility of continuing the clinical trial should be evaluated.

(6) Risk of tearing the inferior alveolar neurovascular bundle: When cystic lesions are severely attached to the nerve, there is a risk of nerve tearing when separating the mass, resulting in postoperative damage to the inferior alveolar nerve and numbness

of the lower lip. When intraoperative nerve tears occur, intraoperative neuroanastomosis should be performed to preserve nerve function as much as possible.

(7) Risk of serious infection after surgery: When the scope of cystic lesions is too large, the risk of postoperative infection increases, and the wound in the operative area may not heal in one stage. In severe cases, it may spread to neighboring tissues, resulting in infection of the maxillofacial space. In the case of severe infection, anti-infection treatment should be actively applied. In the case of infection of maxillofacial space or severe edema of surrounding tissue, the existence of indications for incision and discharge of pus should be considered, and the vital signs of patients should be closely monitored.

IX. Data collection and management

